PROTOCOL NAME:

Details of sponsor

Ms.[name]

Research Governance

Research and Enterprise Directorate

Queens University Belfast

[name]

[name]

Email: [contact]

Chief Investigator & Research Team Contact Details

Chief Investigator:

[name]

Centre for Public Health

Royal Victoria Hospital

[name]

[name]

[contact]

Email: [contact]

Co-Investigator:

[name]

Belfast Health and Social Care Trust

Royal Victoria Hospital

[name]

[name]

Email: [contact]

Co-Investigator:

[name]

Psychology Department

University of Sussex

[name]

[name]

[contact]

Email: [contact]

Purpose:

To validate a newly developed battery of performance-based tests of visual function to be presented using virtual reality. The tests are intended as potential outcome measures for clinical trials of treatments of eye disease: they measure visual performance in patients with low vision on visual tasks that are relevant for daily life.

Introduction:

The ability of patients to perform vision-related daily living tasks is often a desirable metric for assessing the success of a new therapeutic intervention, particularly for making cost-effectiveness decisions. Next generation virtual reality (VR) technology offers the potential to provide customized and standardized naturalistic environments to test patients safely on performance-based measures of visual function for use in assessing the outcomes of clinical trials. We will develop such performance-based measures of visual function in VR and trial them on patients with low vision who have sight impairment.

There is a clear need for improved protocols for assessing the outcomes of clinical trials. Visual performance measures are the most relevant outcome measures for treatment of visual disease, because they capture the visual skills that are most relevant for patients' daily lives. However, because such measures are expensive, and difficult and time consuming to implement and analyse, clinical trials typically rely on standard optometric measures like visual acuity, and on patient answers to quality of life questionnaires. Both of these have significant drawbacks: Standard optometric measures may not correlate well with functional visual ability in various eye pathologies. Questionnaire-based quality of life measures are subjective, may not well isolate visual function, and may correlate poorly with objective measures of visual performance. In a minority of trials where performance measures are used the complexity and expense of generating custom physical environments in which to measure visual performance may preclude multi-centre designs. For the patients, measures of visual performance in physical environments may carry increased risk of falls or accidents or provoke anxiety. For researchers, the increased risks can make it difficult to get approval for real-world studies.

VR offers the potential to provide a step-change in the way clinical outcomes are assessed, by providing custom interactive assessments of visual performance, offering the advantages of complex and naturalistic visual environments without the expense and potential risks to patients. Visual performance data generated in a VR environment could be gathered and analysed automatically, e.g. using hand movements, eye movements or verbal responses, or using motion vectors on a

treadmill for visually guided navigation. The potential to provide custom standardized VR environments in which to measure visual performance has clear potential for use as outcome assessments in multi-centre trials.

The project team have developed custom performance-based tests of visual function in a VR environment, testing skills including object search, clock face and symbol recognition, recognition of gestures and visually guided action. In the current study we propose to pilot the test battery on healthy able-bodied low-vision patients with bilateral ocular disease. Disease selection will reflect the differing types of visual function loss demonstrated by low vision patients; Central loss (e.g. Stargardt's disease); Peripheral loss (e.g. advanced retinitis pigmentosa), and diffuse loss (e.g. Albinism).

Aims of the Research Project:

1. To validate a new virtual reality (VR)-based battery of performance-based tests of visual function that are relevant for patients' daily lives.
2. To quantify the reproducibility of the performance-based tests.
3. To gather acceptability and ease-of-use data from patients.

Experimental Plan

The test battery.

The test battery, developed by [name] at the University of Sussex, incorporates the following tasks

Object search. Participants identify 30 common household objects (e.g. cups, plates, cutlery) placed in a cluttered simulated living room. An infra-red and optical sensing device (Leap Motion, San Francisco, CA) to detect users' hands and project an image of the hands in real time into the virtual environment. Participants indicate the positions of objects they are instructed to identify by pointing to them in the virtual environment.

Box search. In a variation on the object search task, participants are required to indicate the locations of a series of boxes, one presented on each trial. The boxes have a variety of sizes and colours.

Clock face recognition. Patients view analogue clock hands with circular clock faces. Participants are required to tell the time by a verbal response, which is recorded by the tester. According to the responses, the size of the clock face alters on subsequent trials along a logarithmic scale in an adaptive staircase procedure. The performance measure is the size of clock face at which the participant is able to correctly tell the time.

Gesture recognition. Stimuli are short animations of an avatar performing common gestures including pointing, waving, beckoning, shush and stop⁷. Patients are required to describe the gesture, and performance is recorded by the tester.

Visually guided action. In this test an avatar rolls a ball towards the patient across a table in the virtual environment. The ball is rolled at random angles and at 5 different speeds. Participants are required to intercept the balls using images of their hands projected into the virtual environment (using the Leap motion developer kit). Performance is measured as the number of accurate interceptions as a function of ball speed.

Pilot Testing with low-vision patients.

[name] and [name] will arrange to pilot our performance-based tests of visual function on 20 patients with low vision aged 20-50, including patients with Stargardt's disease, advanced retinitis pigmentosa and Albinism. All patients will have colour fundus images and OCT scans taken to enable accurate phenotyping. They will each attend the Northern Ireland Clinical Research Facility (NICRF) for 2 x 2-hour sessions. They will be assessed in both sessions on all five performance-based measures, allowing us to monitor the consistency of our measurements across two time-points. We will also gather qualitative data on ease of use and patient comfort. We have chosen to use young patients in this study because they may be more comfortable with using virtual technologies. We hope to explore applications with older patients in future studies.

Study Procedures

Inclusion Criteria:

1. Male and female participants
2. Age 20-50
3. Bilateral sight impairment due to Stargardt's disease, retinitis pigmentosa or albinism.
4. Sight impairment criteria are as follows:
 - Visual acuity of 3 / 60 to 6 / 60 with a full field of vision.
 - Visual acuity of up to 6 / 24 with a moderate reduction of field of vision

Exclusion Criteria:

1. Any physical impairment that would make use of the virtual reality headset difficult or unsafe.
2. A history of vertigo or dizziness.

Clinic Visit 1 and 2:

1. Seeking Consent: The Research Optometrist will take consent. The information leaflet on the study will be given to potential participants at their low vision appointment. After participants have had sufficient time to gauge their involvement we will acquire written informed consent.
2. Demographic Questionnaire (Appendix 1)
3. Habitual Visual Acuity: LogMAR visual acuity will be recorded for each eye with their normal refractive corrections (glasses or contact lenses in place).
4. NEI VFQ 25- interviewer administered version.
5. Virtual Reality Tests – sufficient time will be given to enable the participant to adjust to the headset and the new tasks.
6. Questionnaire on ease of use and acceptability (Appendix 2)
7. Colour Fundus photographs and Optical Coherence Tomography Retinal Scans.

The total study visit should take approximately 2 hours. Given that the protocol only includes non-invasive visual function tests, the participant should experience minimal pain, discomfort or distress. The tests do require concentration and some participants may find them boring. Some users of VR headsets have reported nausea or dizziness during use so the participant will be warned about this and asked to report if either of these symptoms occur. The test would then be aborted.

Sample Size

This is a small pilot study and therefore we haven't attempted to undertake a formal sample size calculation. However we feel the sample size chosen is sufficient to identify any key issues with using this technology with participants with low vision and also to give some indication of the repeatability of the tests.

Statistical Analysis

Given the pilot nature of this study limited statistical analysis will be undertaken. Greater weight will be given to the responses to the ease of use and acceptability questionnaire. Bland and Altman analysis will be used to investigate the repeatability of the tests.

Visual performance tests in virtual reality using the Oculus rift.

Participants will complete a variety of tasks to assess their visual performance in situations equivalent to those they encounter in daily life. Tests are run via the software Unity and participants are guided through each task by the optometrist.

Study Plan

Activity	Visit 1	Visit 2
Informed consent ¹	X	
Demographics/Medical history	X	
NEI VFQ	X	X
Visual Acuity	X	X
VR test	X	X
Retinal Imaging	X	X
Ease of use questionnaire	X	X

1 Must be dated/signed prior to performing study procedures

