Navigate to the second scene “catch task”. Start the scene. The GUI for entering the data is in Display 1 (see top left corner of Game tab to switch display if it's not already there). Enter the participant tag. Ask participant if they feel if they are at a natural height (above table, not floating below or too high above ground). According to the participant’s response, adjust the Y axis on LM Head Mounted Rig (Position). Click Start. (Trials per speed should 5). Click Next Trial to start each trial – the task will end and save results automatically. Click Save Results to save the results and quit early if needed. Sometimes the hands will disappear from the virtual environment if a participant makes a movement out of the range of the Leap’s ability to detect. If this happens, instruct the participant to hold their hands steadily in front of the head set where the Leap is mounted until the hands are recognized again. The hands must be present throughout a trial for the data for that trial to be recorded.

Navigate to the first scene “gestures”. Start the scene. The GUI is in Display 2 (see top left corner of Game tab to switch display if it's not already there). Enter the participant tag. Click next trial to play the next trial. Click replay to play the current trial. Enter a note to record the participant’s verbal response on each trial, and click 'correct' or 'incorrect' to log the participants response. Click Save Results to save.

Navigate to the second scene “object tasks”. Run the “object task” first. The script is in the Scripts object (Object Search Task), Make sure GUI is Display 1. Start the scene. Enter the participant tag. Click Start (on right hand panel). Click Next Trial to begin next trial. On each trial an object appears in front of the participant and they are required to find a matching object elsewhere in the scene and then indicate its location by pointing to it using their virtual hands. The trial ends either when the object is correctly located (and pointed to), or after 30seconds. The object disappears at the end of each trial. A new object appears when “next trial” is clicked. The data is saved automatically once the 30 trials are complete.

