Next run the box search task. The script is in the Scripts object (Varying Object Task). Start the scene. Enter the participant tag. Click Start. The trials work the same way as for the object search task, except that this time there is a black out between trials – in order to mask the visual transient caused by the box appearing on each trial. The data is saved automatically once the 30 trials are complete.

Gently remove the VR headset from the participant's head.

Clean the lenses with the lens cloths provided.

If, for any reason, the participant is unable to complete the tests, record the reason on the acceptability and ease of use questionnaire.

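### Minor: the interception count has a fixed denominator only in fully recorded sessions, so score it on recorded trials and say how short sessions and lost trials are handled.

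*Combined protocol and SAP*

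**What the plan says.** The Visually guided action paragraph of the Experimental Plan has a ball rolled at 5 speeds and gives the outcome: "Performance is measured as the number of accurate interceptions as a function of ball speed". The instructions for the catch task in Appendix 2 (running the tests on the Oculus Rift) supply the trial number, "Trials per speed should 5", so a complete session is nominally 5 x 5 = 25 trials. The total of 25 is my multiplication; the documents do not state it.

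Two features can make the number of recorded trials differ from 25.

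- **Short sessions.** Under Clinic Visit 1 and 2, if nausea or dizziness occurs, "The test would then be aborted". For the catch task, Appendix 2 tells the operator: "Click Save Results to save the results and quit early if needed". The end of Appendix 2 asks for the reason when a participant cannot finish, but gives no scoring rule.
- **Lost hand tracking.** Appendix 2 warns: "Sometimes the hands will disappear from the virtual environment". It links this to movement outside the sensor's range, and adds: "The hands must be present throughout a trial for the data for that trial to be recorded". It does not say whether such a trial is run again. In normal running, "the task will end and save results automatically". For the two search tasks the end point is explicit: "The data is saved automatically once the 30 trials are complete".

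The second listed aim is to quantify reproducibility. The Statistical Analysis section names Bland-Altman analysis for this and gives no rule for incomplete data.

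**The concern.** Bland-Altman analysis takes the difference between a participant's two scores. It reads the mean of the differences as bias and their spread as measurement error. Both readings need the two scores to be on the same scale. A count of interceptions is on the same scale at both visits only if the same number of trials was recorded at each. If one visit yields 15 recorded trials and the other 25, part of the difference in counts reflects exposure, not performance.

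At stake are the repeatability figures for one of the five tests. Short sessions or tracking trouble could also be more common at the first visit, while participants are new to the headset. The artefact would then look like improvement with practice.

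**Working it through.** The plan gives no sample size calculation, interception rate, stopping rate or tracking-loss rate, so there is no figure of its own to reproduce. Everything below except 5 speeds, 5 trials per speed and 20 participants is an assumption.

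**Set-up.** Trials are independent, with the same interception probability p at both visits (no true change). I use p = 0.4 and p = 0.8. Differences are visit 2 minus visit 1, on the 25-trial total.

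**1. Complete sessions.** The variance of the difference is 2 x 25 x p(1-p) = 50p(1-p), which is 12 at p = 0.4 and 8 at p = 0.8.
- Half-width of the limits: 1.96 x sqrt(12) = 6.79; 1.96 x sqrt(8) = 5.54.
- Sampling error of the mean difference with 20 participants: 1.96 x sqrt(12/20) = 1.52; 1.96 x sqrt(8/20) = 1.24.

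**2. One session stopped after m trials, its count used as a full score.** The expected shortfall is (25-m)p. For m = 20, 15 and 10 this is 2.0 to 4.0, 4.0 to 8.0 and 6.0 to 12.0 catches. By speed, a stop at 15 spread evenly leaves 3 of 5 trials each and costs 2p = 0.8 to 1.6 per speed. If speeds were run in blocks, two speeds would have no trials and would lose 5p = 2 to 4 each. The order of speeds is not stated.

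**3. Two of 20 participants (f = 0.10) stop at 15 at visit 1.**
- Mean shift: f x 10p = 0.40 (p = 0.4) or 0.80 (p = 0.8). Both are below the sampling error in step 1.
- Variance: (1-f) x 50p(1-p) + f x 40p(1-p) + f(1-f) x (10p)^2.
  - p = 0.4: 10.80 + 0.96 + 1.44 = 13.20, half-width 1.96 x sqrt(13.20) = 7.12 (from 6.79).
  - p = 0.8: 7.20 + 0.64 + 5.76 = 13.60, half-width 7.23 (from 5.54).

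A harsher scenario was simulated with 400,000 visit pairs. Hit rates varied between patients, and 10% of patients stopped at each visit, at a random point between 5 and 24 trials. The count limits widened from 6.4 to 7.6 at mean p = 0.4 and from 5.2 to 9.7 at mean p = 0.8. On recorded trials (proportion x 25) they were 6.8 and 5.5.

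**4. Tracking loss, only if lost trials are not run again and loss is unrelated to success.** With loss q1 then q2, the count shifts by 25p(q1-q2).
- 20% then 5%: 1.5 to 3.0 of 25, or 0.3 to 0.6 of 5 per speed.
- 10% then 5%: 0.5 to 1.0 of 25, below the sampling error.
- Equal loss: 0.

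**5. What the proportion costs.** Take a constant 20% loss at both visits.
- Count: 1.96 x sqrt(50 x 0.32 x 0.68) = 6.5 at p = 0.4; 1.96 x sqrt(50 x 0.64 x 0.36) = 6.65 at p = 0.8.
- Proportion averaged over 5 speeds, x 25: with n recorded trials per speed, the mean of 1/n (n at least 1) is 0.268. The half-width is 1.96 x 25 x sqrt(2p(1-p) x 0.268/5) = 7.9 at p = 0.4 and 6.4 at p = 0.8.

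So the proportion has wider limits at the low rate and slightly narrower limits at the high one.

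**The case against.** The strongest reply is that a denominator exists: 5 trials per speed. A reader might infer from the outcome definition alone that the measure has no denominator and is faulty as designed. The documents do not support that. In a fully recorded session the score is a count out of 5 at each speed, and count and proportion carry the same information.

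A reader might also infer that partial counts will be analysed as full scores. That is not stated. A test called aborted, with its reason recorded, could as naturally be left out of the analysis, and then step 3 does not arise. Nor may one assume that tracking loss lowers the count in a completed session. The software may continue until 5 trials per speed are recorded; the text is silent.

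Finally, a reader might expect the two scorings proposed below to bracket the true change. They need not. Take p = 0.4 then 0.6, loss of 20% then 5%, and lost trials that would have been catches with probability 0.4 at both visits. The proportion gives 0.58/0.95 - 0.32/0.80 = 0.211 and lost-as-miss gives 0.58 - 0.32 = 0.260. The true change is 0.200, so both are too high.

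The study is also a 20-patient pilot that plans limited statistics and gives more weight to the questionnaire. These points reduce the size of the concern. They do not remove the gap: partial results can be saved, unrecorded trials can occur, and no rule says how either is scored.

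**Conclusion.** The point holds as a minor one. The stated count is comparable between visits only when all trials are recorded at both, and the plan allows sessions where they are not. An artefact follows if partial counts are used as full scores, or if tracking-lost trials are not run again; the documents leave both open.

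For an individual the effect can be large: 4 to 8 catches for a stop at 15, against complete-data limits of 6.8 and 5.5. For the group, with 2 of 20 stopping once, the mean shift is within sampling error. The limits hardly move at p = 0.4 and widen by about 30% at p = 0.8 (7.23/5.54 = 1.31). All of this rests on assumed rates and on a 25-trial total that the plan does not define. It does not show that the reproducibility aim fails. Scoring on recorded trials is nonetheless a better rule than the stated count, and is easily adopted.

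**What to change.** - **Appendix 2, catch task.** Keep a record, by speed and visit, of trials presented, trials recorded, trials lost to tracking and early quits. State whether lost trials are presented again. If the software already saves trial-level data, this may need only an instruction to retain it, provided lost trials can be told apart from trials never presented.
- **Visually guided action and Statistical Analysis.** Define the score as interceptions divided by recorded trials at each speed. Treat trials never presented because of an early quit as missing, not as misses. State whether Bland-Altman analysis is done by speed or on an average over speeds.
- **Sensitivity analysis.** Repeat the Bland-Altman analysis once with tracking-lost trials counted as misses, because a reach outside sensor range may itself reflect poor visual guidance. Do not present the two results as bounds on the true change.
- **Reporting.** Give lost trials and early quits by visit as a usability result, which suits the pilot's purpose.

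The cost is a short log, one extra analysis, and somewhat wider limits on the proportion scale when the interception rate is low (7.9 against 6.5 in step 5). The criteria for stopping a session are not in question and need no change for this purpose.

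### The Purpose and Aim 1 are to validate the VR battery, but the planned analyses cover only acceptability and repeatability

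*Combined protocol and SAP*

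**What the plan says.** The Purpose section opens with "To validate a newly developed battery of performance-based tests of visual function to be presented using virtual reality" and adds that "The tests are intended as potential outcome measures for clinical trials of treatments of eye disease". The Aims section lists three separate items. Aim 1 is "To validate a new virtual reality (VR)-based battery of performance-based tests of visual function", Aim 2 is "To quantify the reproducibility of the performance-based tests", and Aim 3 is to collect acceptability and ease-of-use data.

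Statistical Analysis announces a limited analysis because this is a pilot, and then names two things: "Greater weight will be given to the responses to the ease of use and acceptability questionnaire" and "Bland and Altman analysis will be used to investigate the repeatability of the tests". Sample Size gives no formal calculation. It supports the chosen number as enough to find key problems with the technology and "also to give some indication of the repeatability of the tests". The section on pilot testing explains the assessment at both sessions as "allowing us to monitor the consistency of our measurements across two time-points".

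The Study Plan table schedules visual acuity, NEI VFQ and retinal imaging at both visits, alongside the VR tests. The imaging is said to be for phenotyping.

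**The concern.** The only goal in the Purpose, and the first of the three aims, has no analysis. If the plan is followed exactly, the study will report questionnaire responses and limits of agreement. Neither shows whether a VR score reflects visual function.

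This matters because the tests are meant as possible trial outcome measures, and evidence that they measure vision is what a later user would look for. The gap also leaves room for analyses chosen after the data are seen. Comparator data exist, but no score, visit or expected direction is fixed. Even with a single score per test, 5 tests x 2 comparators x 2 visits = 20 correlations would be available, and the choice among them would be open.

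**Working it through.** **Step 1. Match each aim to its analysis.** The sample size of 20 has no alpha, power, effect size or standard deviation behind it, so there is no calculation to reproduce. The check is to set the sections side by side.

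| Aim | Statistical Analysis | Sample Size rationale |
|---|---|---|
| 1. Validate | none stated | not mentioned |
| 2. Reproducibility | Bland-Altman | some indication of repeatability |
| 3. Acceptability and ease of use | questionnaire, given most weight | key usability issues |

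No section relates VR scores to acuity, NEI VFQ-25, retinal imaging or type of visual loss. No sighted control group, real-world task comparator, validity hypothesis or success criterion is described.

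**Step 2. Can the Aim 2 analysis stand in for Aim 1?** For each patient the Bland-Altman method uses d = (visit 2 score) - (visit 1 score). The limits of agreement are mean(d) ± 1.96 x SD(d). The mean moves with any systematic shift between visits, such as practice, and the SD reflects within-person variation. No external measure of vision enters the formula. A score unrelated to vision could therefore show narrow limits.

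**Step 3. What could a validity analysis deliver with 20 patients?** This concerns a remedy, not an error in the plan. The correlations are assumed values. For a Spearman correlation r, the Bonett-Wright interval is

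tanh( atanh(r) ± 1.96 x SE ), with SE = sqrt( (1 + r²/2) / (n - 3) ).

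For r = 0.5 and n = 20: atanh(0.5) = 0.549; SE = sqrt(1.125/17) = 0.257; 1.96 x SE = 0.504. The limits are tanh(0.045) = 0.05 and tanh(1.053) = 0.78.

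| r (n = 20) | 95% interval |
|---|---|
| 0 | -0.44 to 0.44 |
| 0.3 | -0.17 to 0.66 |
| 0.5 | 0.05 to 0.78 |
| 0.7 | 0.32 to 0.88 |

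The smallest estimate with an interval wholly above zero is about 0.46. The plain Fisher interval, with SE = 1/sqrt(n - 3), gives a similar result: 0.07 to 0.77 at r = 0.5. With 7 patients per disease (assuming a roughly even split of 20 over three diseases), r = 0.7 gives -0.22 to 0.96, so within-disease results could only be descriptive.

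**The case against.** The strongest defence is that the protocol calls itself a small pilot, promises only limited analysis and describes the tests as potential outcome measures. That explains why the analysis is short. It does not reconcile a lead aim of validation with an analysis section that leaves validation out.

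A second defence is that repeatability is one component of validating a measurement. That is true in general, but this protocol lists reproducibility as its own aim, so Aim 1 must mean something more.

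A third is that acuity and NEI VFQ-25 are collected and a comparison is implied. No section says so, and the Introduction itself doubts that acuity and questionnaires track functional vision well. Any comparison would therefore need its expectations stated in advance.

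Two stronger readings are tempting. A reader might infer that the study should have been a full, formally powered validation study. The documents do not support this: a 20-patient pilot is a legitimate design, and nothing in it promises a validation conclusion or criterion. A reader might also infer that the sponsor will present the battery as validated. No section says that; it is a risk created by the wording.

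What stands of the defence is that the mismatch lies mainly between label and plan, and that it can be cured by a change of wording.

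**Conclusion.** The concern holds as a mismatch between the lead aim and the analysis plan. Two of three aims have an analysis; the one without is the sole goal in the Purpose. As written, the plan cannot support a statement that the battery has been validated. This conclusion rests only on the protocol's text and on what a test-retest comparison can show, not on any assumed number.

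It does not follow that the battery lacks validity, or that the study can say nothing about it. Candidate comparators are measured at both visits, so the gap is in the plan and not in the data. The intervals above assume complete data on 20 patients. They show that a validity analysis would be preliminary: only fairly strong associations could be distinguished from zero, and absence of association could not be shown.

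This should be fixed before the data are analysed. It is inexpensive to correct and raises no safety issue.

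**What to change.** **Option A (main recommendation).** Reword the Purpose and Aim 1 to piloting the battery in patients with low vision to assess feasibility, repeatability and acceptability. State in Statistical Analysis that no validation claim will be made. The cost is two sentences reworded and one added; the downside is a more modest aim.

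**Option B (alternative).** Word Aim 1 as preliminary validity and prespecify an exploratory, estimation-only analysis of data already collected. Report 5 x 2 = 10 Spearman correlations with 95% intervals and the number of patients in each. These relate one named score per VR test to habitual logMAR acuity, with one rule for combining the eyes, and to one named NEI VFQ-25 score. Fix beforehand the visit (or the average of visits) and the expected direction. Mark plots by disease type. Make no claims of significance or of no association. The following need settling first:

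- *Clock:* how the threshold size is derived from the staircases.
- *Catch:* the proportion of recorded trials intercepted, with the number recorded. Appendix 2 keeps a trial only if the hands remain present, so a raw count would mix tracking loss with performance.
- *Gestures:* the proportion correct, with the number of trials and the handling of replays fixed. Appendix 2 allows replay and gives no number of trials.
- *Object and box search:* confirm which variables the software saves, then name one for each task.
- *Acuity:* reconcile two conflicts, which are separate matters but affect this comparator. The Clinic Visit section records acuity in habitual correction, while Appendix 1 (1.1 and 1.6) describes refraction and a trial frame. Section 1.6 triggers the 1 m test below 15 letters at 4 m, while 1.7 adds a 1 m score below 20 and 30 letters above 20. Scores of 15 to 19 therefore call for a 1 m result that 1.6 does not require, and exactly 20 has no rule.

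Add a caution that eligibility mixes patients with full and reduced fields and no field test is scheduled, so pooled correlations with acuity may be distorted.

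Option B needs no new visit or test. Its downsides are wide intervals and more specification work than a few paragraphs.
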